
Zoledronic Acid: Initial trial data and clinical pharmacology

Zoledronic acid demonstrates superior pharmacodynamic properties for suppression of the primary bone resorbing cell, the osteoclast, in comparison to actions of earlier generation oral and IV bisphosphonates⁵⁹. Zoledronic acid has a particularly high affinity for binding to the calcium phosphate bone mineral, hydroxyapatite. Binding localizes to regions of high bone turnover, specifically trabecular

bone. Within the osteoclast, zoledronic acid inhibits a key regulatory enzyme known as farnesyl diphosphate synthetase which is 17 times more effectively than alendronate and 67 times more than pamidronate^{59,60}. Zoledronic acid in the 5 mg dose is now an option for treatment of post-menopausal osteoporosis in patients with advanced disease who may have failed less aggressive therapies, including treatment with other bisphosphonate drugs. This medication is administered IV once annually and has the advantage of single time administration.

Side Effects of Zoledronic Acid

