Due to the potency of IV ZA, adverse effects of the agent may occur. The most common side effects of ZA are an acute phase reaction involving fever (15%), myalgias (8%), flu-like illness (7%), headache (6%) and arthralgias (5%)^{61,62}. In rare cases, patients may experience noncardiac chest pain (1/3%). Because infusion of IV ZA can cause an increase in serum creatinine up to 30 days post treatment, the drug should be avoided in persons with creatinine clearance <35 mL/min. An association between atrial fibrillation and IV ZA use was observed in a large study of over 7000 patients⁶². The FDA subsequently conducted an investigation, comparing results of the prior trial to other studies of IV ZA, and concluded that no clear relationship could be identified between bisphosphonate use and atrial fibrillation⁶³. Both oral and IV bisphosphonates have been associated with osteonecrosis of the jaw (ONJ), but further review of the data by the American Dental Association found that incidence of ONJ is rare in post-menopausal women with osteoporosis but more common in those with monthly infusions for cancer treatment⁶⁴. This group recommended no special treatment beyond routine dental care for those using IV ZA for osteoporosis. Finally, several reports of low trauma fractures of the femur have been observed among patients primarily over age 60 who are prescribed chronic bisphosphonate treatment (2.5-8 years)^{61,65}. A recent cohort study of over 1.1 million patients by Dell et al. found that while duration of use of bisphosphonates was correlated with incidence of atypical femur fractures, (particularly beyond 5 years of use), no correlation with age and duration of use was found.⁶⁶ Because our study will involve only a single dose of ZA, we do not anticipate observing the above effect from the drug alone. Based on these new findings, we also believe that individuals ages 61-65 should not be excluded by age alone.

Previous Clinical Trials of Zoledronic Acid

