- Completion of the World Health Organization (WHO) Fracture Risk Assessment Tool (FRAX)⁷³. The FRAX asks for information about age, date of birth, sex, weight, height, previous fracture history, parental fracture history, smoking, steroid use, history of rheumatoid arthritis, presence of a medical condition related to osteoporosis, alcohol use, and current hip bone mineral density (see data collection forms in Appendix B). All data are then entered into the FRAX website (available through the WHO) to obtain the 10 year probability of a fracture. No personal identifiers are used and no data is saved on the website.
- Collection of blood sample for pre-treatment levels of PINP as measures of bone formation, s-CTX as marker of bone resorption, IL-1 β as a pro-osteoclastogenic factor, CPK (Creatinine Phosphokinase) as a marker of muscle tissue and kidney function, and serum calcium. DXA scan, to be obtained as soon as the subject is medically stable for testing off the intensive/acute care floor (may be done up to 7 days after the infusion of study drug).

C. Study drug infusion: Post injury day 21

Within day 21 post injury, subjects will be administered study drug and assessed as follows:

- Measurement of serum calcium level to ensure therapeutic levels.
- A single IV infusion of ZA 5 mg or a placebo drug with the same dilution and duration of administration (prepared and dispensed by the TJUH IDS).
- The single IV infusion will be administered over a 2 hour period (2.5 mg per hour)
- Supplemental hydration as needed to keep urine output > 2000 cc per day from the day prior to study drug administration until 3 days post-infusion.
- Acetaminophen 650 mg every 4 hours for the 24 hour period following drug administration. This is intended to reduce the frequency and severity of fever or myalgias associated with ZA administration⁶¹.

D. Days 1-7, Post Drug Infusion

- After the first day, acetaminophen will continue to be offered as needed every 4 hours through day 3 post-infusion.
- Supplemental hydration will be continued as needed to keep urine output > 2000 cc per day until 3 days post-infusion
- Subjects will be assessed daily for 3 days, then weekly for one month after study drug administration for known side effects of the drugs, including myalgias, fever, gastrointestinal disturbances, and flu-like symptoms.

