- Subjects will be assessed for participation in physical therapy and occupational therapy since receiving the study drug, as well as willingness to get study drug again via interview held 7 days following infusion.

E. Days 1, 3, 7, 14, Post-Drug Infusion

- Subjects will be assessed weekly for one month after study drug administration for known side effects of the drugs, including myalgias, fever, gastrointestinal disturbances, and flu-like symptoms.
- Laboratory values will be drawn for serum calcium, phosphate, and magnesium.

F. Month 1 Post Injury (+/-4 days)

- Subjects will be assessed weekly for one month after study drug administration for known side effects of the drugs, including myalgias, fever, gastrointestinal disturbances, and flu-like symptoms.
- Blood samples* for laboratory values will be drawn for s-CTX, IL-1 β , 25-OH vitamin D, serum calcium, intact parathyroid hormone, and Serum P1NP. *The total amount of blood drawn for all laboratory tests will be < 25 ml at each data collection session.

G. Month 2, 6 & 10 Post Injury

A patient questionnaire will be administered either in-person or by telephone. The questions cover:

- Any evidence or knowledge of bone fractures since the previous contact.
- Information about exercises and standing, including use of functional electrical stimulation (FES), such as how often and average daily duration.
- Supply of vitamin D and calcium tablets with reminder to bring pill bottles with them to clinic for follow up assessments and study sponsored refill of medications. At these follow up visits, pill counts will be done to assess their compliance with medication use.

H. Months 4 & 12 Post Injury

- Blood sample will be drawn for s-CTX, 25-OH vitamin D, serum calcium, intact parathyroid hormone. Serum P1NP will also be drawn at 4 months. The total amount of blood drawn for all laboratory tests will be < 25 ml at each data collection session.
- Complete neurological exam (at 12 months only)
- A patient questionnaire will be administered.
- DXA scan

I. Month 8 Post Injury

- Blood sample will be drawn for 25-OH vitamin D and serum calcium. The total amount of blood drawn for all laboratory tests will be < 25 ml at each data collection session.

J. Serum 25-OH Vitamin D Monitoring and Supplements

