Analyses of the distal femur and proximal tibia will be conducted as described by Modlesky⁷⁰⁻⁷⁴ and Shields⁷⁵. For the distal femur analysis, the distal edge of the DXA region of interest box will be placed at 13% of femur length and the proximal edge will be placed at 20% of femur length. For the proximal tibia, the same sized region of interest box will be placed immediately above the fibular head and extend distally (Figure 3).

Figure 3: DXA scans and region of interest for distal femur (A) and proximal tibia (B)

6. Safety Monitoring

Subjects will be interviewed daily for 3 days, then weekly for one month after study drug administration for any side effects of treatment, in particular, fever and myalgias, using a standardized interview form. Adverse events will be recorded and followed until resolution. A serious adverse event will constitute any event that is life-threatening, requires hospitalization, results in death or disability, requires intervention to prevent permanent impairment or damage, or results in a congenital anomaly. Important medical events that may not result in death, be life threatening or require hospitalization also may be considered to be a serious adverse event when, based on appropriate medical judgment, they may require medical or surgical intervention to prevent one of the outcomes listed in this definition. The PI will report all serious adverse events to the Safety Monitoring Board, the Jefferson IRB, and the project officer at NIDRR.

7. Data and Safety Monitoring Board (DSMB)

The DSMB will be recruited from Jefferson Medical College (JMC) faculty members and charged with monitoring study compliance. They will review screening and enrollment procedures, data collection and analysis, reporting of adverse events, and subject safety. The DSMB members will meet every 6 months or more frequently as needed. The study investigators will meet with the DSMB chair every 6 months to review recommendations or concerns.

The DSMB will be composed of the following members:

[name] [name] (Chair)	Professor of Rehabilitation Medicine
[name]	Assistant Professor of Medicine, Division of Endocrinology
[name]	Clinical Assistant Professor of Medicine, Division of Nephrology

E. Data Analysis

1. Evaluation of Baseline Characteristics

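### No adverse event question is specified after the first month post-infusion, and the end of AE and SAE collection is not stated

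*Combined protocol and SAP*

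**What the plan says.** Section D.3, Safety Monitoring, sets the period of active questioning: "Subjects will be interviewed daily for 3 days, then weekly for one month after study drug administration for any side effects of treatment". The study activities for the days after infusion give the same period, aimed at expected reactions: "Subjects will be assessed daily for 3 days, then weekly for one month after study drug administration for known side effects of the drugs".

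On recording and reporting, Safety Monitoring adds "Adverse events will be recorded and followed until resolution" and "The PI will report all serious adverse events to the Safety Monitoring Board, the Jefferson IRB, and the project officer at NIDRR". Neither sentence has an end date. The SAE definition includes death, hospitalization, life-threatening events and congenital anomaly. On oversight, the DSMB section says "The DSMB members will meet every 6 months or more frequently as needed", and its remit includes the reporting of adverse events.

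The later contacts are described in three places:
- **Months 2, 6 and 10** (study activities): the questionnaire opens with "Any evidence or knowledge of bone fractures since the previous contact", then turns to exercise, standing and electrical stimulation, and to the supply of vitamin D and calcium.
- **Every two months in year 1** (Subjective reports): fractures, exercise and standing.
- **Table 5** (year 1 every two months, then six-monthly in years 2 to 4): fractures, supplements, exercise and other treatments, functional status.

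Table 4, the visit schedule, has no adverse event row. The month 4 and 12 visits include a questionnaire whose content is not given there.

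The background section on side effects states "Both oral and IV bisphosphonates have been associated with osteonecrosis of the jaw (ONJ"), and also discusses an atrial fibrillation signal and low-trauma femur fractures. Safety and tolerability is a named secondary outcome in the Project Summary.

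**The concern.** The plan obliges the investigator to report every SAE, but after the first month it specifies no step that would bring one to light, other than a fracture. The sentence on following events to resolution helps only with events already recorded.

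The protocol gives its own reason to doubt spontaneous reporting. In the background it says that fracture figures may be too low because many patients go to local hospitals and not to specialist SCI centers. That remark concerns fractures. Extending it to an admission for arrhythmia or a jaw problem is an inference, but a natural one.

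At stake is what a late SAE count means. A report of no jaw events or arrhythmias after month 1 could not be told apart from nobody having asked, and the DSMB would see solicited data from each subject's first month only.

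**Working it through.** **1. Arm sizes.** The point disputes none of the plan's figures; the sample size is reproduced only to fix the denominators. Half of a 29% loss over an SD of 13% gives 14.5/13 = 1.12, and half of 8% over 3% gives 4/3 = 1.33, matching the stated 1.1 and 1.3. A two-sample t-test with 2:1 allocation, two-sided 5% and 80% power, rounded up to whole 2:1 multiples, gives 24, 33 and 39 for effect sizes 1.3, 1.1 and 1.0, exactly as stated. Enrolling 48 at 2:1 gives 48 × 2/3 = 32 ZA subjects. The plan's 18% dropout leaves 39, of whom 39 × 2/3 = 26 are on ZA.

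**2. When questioning stops.** Baseline assessment runs from day 8 to day 21 and infusion is due by day 21, so infusion is taken to fall between days 8 and 21. One month later is about day 8 + 30 = 38 to day 21 + 30 = 51 after injury. The first later contact, at month 2, falls at about day 61, after questioning has ended.

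**3. Coverage**, with a month of 365.25/12 = 30.44 days:
- Infusion to month 12: 30.44/(365.25 − 8) = 8.5%, or 30.44/(365.25 − 21) = 8.8%.
- Infusion to month 48: 30.44/(1461 − 8) or 30.44/(1461 − 21), both 2.1%.

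These are shares of calendar time, not of missed harm.

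**4. Contacts after questioning ends.** Year 1: months 2, 4, 6, 8, 10 and 12, which is 6. Years 2 to 4 in Table 5: 2 × 3 = 6. The total is 12 at most, because enrollment runs over 4 years of a five-year timetable and later contact is limited to the grant cycle. Late enrollees will have fewer.

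**5. Which named risks a later contact asks about:**

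| Risk in the background section | Listed means of finding it after month 1 |
|---|---|
| Creatinine rise | Placed within 30 days, so not a late risk |
| Low-trauma femur fracture | Asked at each contact; permission sought for x-ray reports and mechanism |
| Jaw osteonecrosis | None listed |
| Atrial fibrillation | None listed |

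Other admissions, serious illness and pregnancy are likewise not listed.

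**6. What better questioning could show.** The documents give no late event rate for this population, so the rates below are assumptions. The chance of at least one case among n ZA subjects is 1 − (1 − p)^n.

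| Assumed rate p | n = 32 | n = 26 |
|---|---|---|
| 1 in 10,000 | 0.3% | 0.3% |
| 1 in 1,000 | 3.2% | 2.6% |
| 1% | 27.5% | 23.0% |
| 2% | 47.6% | 40.9% |
| 5% | 80.6% | 73.6% |

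With zero events, the one-sided 95% upper bound is 1 − 0.05^(1/n): 8.9% for n = 32 and 10.9% for n = 26.

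**The case against.** The strongest reply is that SAE reporting is open-ended. No date closes it, admission and death are within the definition, and the DSMB looks at adverse event reporting twice a year. Subjects return for scans and blood tests at months 4 and 12 and for blood tests at month 8, are interviewed every two months, and belong to a center that offers lifetime care. A death would normally surface when a contact fails. This stands as far as it goes: the text permits passive reporting throughout. It does not supply a question that would prompt a report.

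Second, the forms are in Appendix B, which is not in the text, and the month 4 and 12 questionnaire is not described there. An adverse event item on a form cannot be excluded. Table 5's year 1 column does list topics for the two-monthly contacts, however, and adverse events are not among them.

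Third, the background plays these risks down. Jaw osteonecrosis is called rare in post-menopausal osteoporosis and more common with monthly cancer infusions, and the regulator found no clear atrial fibrillation link. Recent dental surgery and facial fractures needing oral surgery are exclusions. All true, and together with the small sample this rules out any argument from detection power.

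Fourth, Aim 3 tests only early tolerability: symptoms over three days, therapy in the first week, and willingness to be treated again. No long-term safety claim is planned, so it would be speculation to say that an absence of events will be presented as proof of safety.

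**Conclusion.** The point holds as a gap in data collection. After one month post-infusion no adverse event question is specified, no end to AE or SAE collection is stated, and non-fracture serious events depend on spontaneous reports. About 91% of the time from infusion to month 12 is without solicited questioning, and up to 12 planned contacts go unused for it. This should be corrected, but it does not threaten the primary analysis or the sample size. The conclusion assumes that the listed contact topics are complete and that Appendix B holds no adverse event item.

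Three stronger readings are tempting and not supported:
- **Late risks named in the protocol cannot be seen.** Femur fracture is actively asked about, and the other events can still be reported. They are not solicited, which is a narrower statement.
- **Late SAEs would reach the DSMB only by chance.** Repeated structured contact and an open-ended reporting duty make capture incomplete, not accidental.
- **One month is too short because "This medication is administered IV once annually".** A dosing interval describes administration. It does not show when harms appear.

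**What to change.** 1. Add a short fixed question block to the existing interviews at months 2, 4, 6, 8, 10 and 12 and to the six-monthly contacts in Table 5: any hospital admission or new serious illness, any jaw or dental problem, any diagnosed arrhythmia, and any pregnancy. The pregnancy item is useful because the SAE definition includes congenital anomaly while pregnancy is tested only at screening.
2. State in Safety Monitoring that SAEs are collected from infusion through month 12, and name the reduced set collected afterwards, for example deaths, jaw events and pregnancy outcomes.
3. Tabulate these events by arm under Aim 3, with the number of subjects actually asked at each contact as denominator.
4. If the Appendix B forms already contain such questions, cite them in Safety Monitoring and add an adverse event row to Tables 4 and 5.

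The cost is a few minutes at contacts already planned, a revised questionnaire and one more table. No visit is added and the sample size does not change. The drawback is that more background complications of spinal cord injury will be recorded and must be classified. In return, late SAEs are ascertained completely and in the same way in both arms, so that none recorded means none reported when asked.

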A. Screening: Post injury days 0-17

- Subjects admitted to the RSCIC with suspected complete SCI will be approached for participation shortly after admission. After providing informed consent, subjects will be screened between 0 and 17 days post injury. The screening will review of the medical record medical/surgical history and physical/neurological examination performed according to ISNCSCI guidelines to ensure an AIS Grade A SCI is present, or post-menopausal) and social or lifestyle factors that could alter ability to participate.
- A serum pregnancy test (for females of child bearing age).
- Standard of Care laboratory tests of kidney (TJUH Basic Metabolic Panel) and liver function (TJUH Hepatic Panel) will be reviewed to ensure the patient does not have a history of chronic liver or kidney failure, unknown to family or subject or not revealed on subject history interview.

- Serum calcium measurement. If initial serum calcium is <7.0 mg/dl, the subject will be given correctional calcium doses in accordance with standard hospital treatment protocol for subjects with critically low calcium levels. The subject may still be able to participate if the calcium level is corrected by the day prior to study drug infusion.
- Serum Vitamin D measurement. Subjects with initial vitamin D levels in the deficient range (<13ng/ml) will not be eligible for participation. If subject's 25-OH vitamin D is between 13 and 20, the subject will be supplemented with high potency oral ergocalciferol 50,000 International Units (IU) per week until retesting occurs at 4 weeks. At the time the screening value is returned, subjects with 25-OH vitamin D levels between 20 and 32 will be started on 2000 IU vitamin D daily and those with levels 32 and higher will be initiated on 1000 IU daily. Supplemental oral calcium of 1200 mg daily will be started on the same day as the vitamin D, except in cases of low values as described above.
- Intact Parathyroid Hormone (iPTH) measurement.

B. Baseline Assessments: Post-injury days 8-21

A Baseline Assessment will be completed between 8 and 21 days post-injury, and include the following:

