Information on Physical Examinations and Clinical Assessments

Objective Evaluations: To ensure the patient has a complete spinal cord injury (AIS Grade A), investigators will perform a complete neurological exam according to ISNCSCI guidelines as part of initial screening (days 2-17 post injury). A confirmatory exam will be conducted in the 24 hours prior to study drug delivery. At the end of the study when the patient returns for final laboratory tests and DXA scan, a repeat neurological examination will be performed.

Subjective reports: Interviews will be conducted with patients every 2 months during the first year, either in person if testing is scheduled, or by phone between testing sessions. The first phone call will occur 2 months from injury if the subject is not an inpatient or not available for in-person interview. During these interviews, subjects will be asked about any evidence or knowledge of bone fractures since the previous contact. We will obtain information about exercises and standing, (including use of FES), such as how often and average daily duration.

Follow up for Subsequent Years of Grant Cycle

During the subsequent years of the grant cycle, patients will be contacted every 6 months for information on fractures sustained in the prior 6 months. As part of the consent form, we will be requesting permission to receive x-ray reports of any bone fracture experienced and mechanism of injury between years 1 and 4 post injury and collect information on participation in standing, lower extremity exercise and functional electrical stimulation (FES), and current calcium and vitamin D use.

[figure not shown]
Early Termination

Should a subject gain neurological function prior to initial drug administration and no longer have a complete SCI, that potential subject is withdrawn from the study. Should a subject recover neurological function and the SCI be deemed incomplete any time after the study drug has been administered, that participant will continue with all assessments and follow up studies without exception.

5. DXA Scan Analyses

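### The serious adverse event definition omits prolongation of an existing hospital stay, although subjects are, by inference, inpatients when drug effects are expected

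*Combined protocol and SAP*

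**What the plan says.** All references are to the combined protocol and SAP.

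Section D.3, item 6 (Safety Monitoring) opens the definition with "A serious adverse event will constitute any event that is life-threatening, requires hospitalization, results in death or disability" and completes the list with "requires intervention to prevent permanent impairment or damage, or results in a congenital anomaly". A further sentence covers important medical events that meet none of the main criteria. These "also may be considered to be a serious adverse event when, based on appropriate medical judgment, they may require medical or surgical intervention". The clause also limits the purpose of that intervention, which has to be "to prevent one of the outcomes listed in this definition". Prolonging a hospital stay is mentioned neither here nor elsewhere.

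The same section has the investigator report all serious adverse events to the safety board, the IRB and the funder's project officer. Adverse events of any grade are recorded and followed up.

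On setting, section D.3, item 4 (Screening) says: "Subjects admitted to the RSCIC with suspected complete SCI will be approached for participation shortly after admission". Study drug is given within 21 days of injury. The baseline DXA is "to be obtained as soon as the subject is medically stable for testing off the intensive/acute care floor", and may follow the infusion by up to 7 days. Under Information on Physical Examinations and Clinical Assessments, the plan allows that a subject may still be in hospital at the first two-monthly contact: "The first phone call will occur 2 months from injury if the subject is not an inpatient".

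**The concern.** A hospitalization criterion works well in outpatient trials, where being admitted marks an event as serious. In a trial that doses people already in hospital, the matching marker is a longer stay, and this definition leaves it out. The gap falls in the weeks when the plan itself expects drug effects.

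Seriousness determines who hears of an event. The only reporting duty from the investigator to the board, the IRB and the funder that the section states is for serious events. An event that keeps an inpatient in hospital for an extra week could be classed as non-serious, while the same event in a discharged subject who is then admitted would be serious. Classification would then depend partly on the discharge date rather than on severity.

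**Working it through.** There is no stated figure to reproduce. The check compares the definition with the setting and with the expected timing of harm.

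**1. When drug effects are expected.** Aim 3 looks for acute reactions over the 3 days after infusion. Section C (Side Effects of Zoledronic Acid) says creatinine may rise for up to 30 days. Infusion is no later than day 21. I assume it is no earlier than day 8, because the pre-treatment blood sample belongs to the baseline window of days 8 to 21.

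- Acute reactions: the window ends between day 8 + 3 = 11 and day 21 + 3 = 24.
- Creatinine: the window ends between day 8 + 30 = 38 and day 21 + 30 = 51.

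**2. Where subjects are at that time.** They are recruited as admitted patients with a complete injury. Some may not be fit to leave the intensive or acute care floor for a scan until after the infusion. Urine output is managed against a daily target from the day before infusion to 3 days after it. Inpatient status is allowed for at 2 months (about 2 × 30 = day 60), which is later than day 51. No sentence says that every subject is an inpatient at dosing, but this is the natural reading for the infusion and the 3 days after it. How many are still inpatients up to day 51 is not stated.

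**3. A test event.** Take a creatinine rise in an inpatient after infusion that lengthens the stay by a week and resolves, without threat to life and without a judged risk of lasting damage.

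- Life-threatening: no.
- Requires hospitalization: the subject is already in hospital, so no admission is newly required.
- Death or disability: no.
- Intervention to prevent permanent impairment or damage: no, by construction. If treatment were judged protective, the event would qualify.
- Congenital anomaly: no.
- Important medical event: optional, and tied to preventing a listed outcome. A longer stay is not one.

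No firm criterion is met. If the same event brings a discharged subject into hospital, the hospitalization criterion is met at once.

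**4. Number exposed.** With 48 subjects randomized 2:1, 48 × 2/3 = 32 receive zoledronic acid and 16 receive placebo. The rule applies to both arms alike. These are the most subjects to whom the gap could apply, not a count of events. The plan gives no rate for events that lengthen a stay.

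**The case against.** The other side has substantial points, and most of them limit the concern.

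- A reader might infer that the hospitalization criterion can never be met in the early period. The documents do not support that. A separate rehabilitation hospital is affiliated with the centre (Study Location and SCI Population), and a return from there to acute care, or a readmission after discharge, could reasonably be counted. An investigator might also read the criterion as needing hospital-level care. The plan settles neither the transfer question nor that reading, which is itself a reason to clarify it.
- The criterion on intervention to prevent permanent impairment is firm and applies to inpatients. Many renal or calcium events that are treated would come in through it, or through the important-medical-event clause.
- A reader might infer that the safety aim rests on a serious event count that will be too low. It does not. Aim 3 compares acute symptoms, therapy participation and willingness to be treated again, and none of these depends on seriousness.
- Safety data are not lost. Side-effect interviews run daily for 3 days and then weekly for a month. The board reviews adverse event reporting every 6 months, or more often if needed, and has nephrology and endocrinology members. The section also does not say that non-serious events are never passed on.
- The plan allows for inpatient status at 2 months. It does not say that it expects it.

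All of these stand. What they leave is an event that lengthens the stay, threatens no listed outcome and needs no protective intervention. Nothing in the definition makes that event serious.

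**Conclusion.** The omission is certain from the text. The consequence is a risk of under-classification and slower reporting to the safety board, the IRB and the funder. It rests on the inference that most or all subjects are inpatients at infusion and for some time after it. The inference is strong for the 3-day window and weaker for the full 30 days. That reporting would be slower is also an inference, since the section sets no time limit for reporting serious events.

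The size cannot be stated, because no event rate is given. The documents do not support saying that serious events will be under-reported, only that some could be. Sample size, power, significance level and every planned analysis are unchanged. The point is worth acting on because the rule as written can classify the same event differently according to discharge date, and the correction is simple.

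**What to change.** In section D.3, item 6, change the criterion to *requires hospitalization or prolongation of existing hospitalization*. Add a short statement that a return from rehabilitation to acute care because of an event counts. Because the important-medical-event clause refers back to the outcomes in the definition, it will then cover a longer stay without further change.

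The cost is a small protocol amendment. The downside is some extra serious event reports that reflect complications of the injury rather than the drug, at one site with 48 subjects.
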